Specific Aim #3: To assess complication rates and long term outcomes for infants receiving VTV versus PLV.

Objectives:

- To compare the total duration of neonatal resuscitation before reaching a stable state ready for transfer to NICU from the DR
- To record APGAR scores as a means to evaluate the ongoing resuscitation
- Compare oxygen requirements between VTV and PLV group during DR resuscitation
- To assess the incidence of complications including pneumothorax
- To evaluate for other unexpected adverse events that may be associated with VTV
- Evaluate longer term pulmonary morbidities: duration of invasive ventilation, BPD rates, and home oxygen requirements at discharge.

DESIGN AND PROCEDURE

EXPERIMENTAL DESIGN

Phase I: Phase I will be an observational, non-interventional study. All infants will receive routine resuscitation as recommended by the NRP. A flow sensor device connected to Respironics NM3 monitor (*Philips Healthcare, Eindhoven, Netherlands*), will be placed between the ETT and T-piece resuscitator to measure breath to breath tidal volume. Providers will be blinded from the actual TV measurements as in routine clinical scenario, and no intervention will be recommended or planned based on the TV measurements.

We will select a convenience sample of 10 patients. All preterm infants born < 32 weeks at Baystate Medical during the 1 year study period will be screened for possible inclusion.

Phase II: We will conduct a randomized control trial to assess feasibility of VTV in the delivery room compared to PLV in preterm infants.

SELECTION OF SUBJECTS

All preterm infants born < 32 weeks at Baystate Medical Center during the 1 year study period will be screened for possible inclusion. With annual delivery of approx.4000 infants, of which 80-100 infant born < 32 weeks gestation, there will be sufficient patient population for the proposed pilot study.

Inclusion Criteria:

- Gestational age < 32 weeks of gestation
- Infant born at Baystate Medical Center
- Requiring intubation and positive pressure ventilation in the delivery room
- Parental Consent

Exclusion criteria:

- Maternal prolonged rupture of membrane > 2 weeks duration
- Known congenital or cardiac abnormalities or discovered in the immediate neonatal period.

Withdrawal/Termination Criteria:

- Withdrawal of parental consent

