PHASE I: No specific withdrawal/termination criteria will be required as this is an observational study to assess feasibility of measuring tidal volume in the DR. Infant will continue to receive routine care as recommended by NRP, even if TV measurements are unsuccessful.

PHASE II: Control Arm: No specific withdrawal/termination criteria will be required, as these infant will continue to receive routine care per NRP recommendations without any study related intervention.

Intervention Arm: If TV cannot be measured or VTV cannot be provided within 60 seconds of initiating PPV via the ETT, the infant will be automatically switched to receiving routine care as recommended by the NRP.

INFORMED CONSENT PROCESS AND TIMING

Who: Parent.

When: "Deferred consent" is being requested after the birth of the child. The study process starts as soon as the baby is born and requires intubation as determined by the clinical team providing resuscitation. We will obtain a deferred consent from the parents only if the baby requires intubation in the delivery room and the TV measurements were obtained. We will approach the parents to use the data that was collected in the delivery room.

Rationale for deferred consent: *In an ideal situation, the consent should be obtained prior to study intervention. However, since the study intervention starts within few seconds to minutes of the baby's birth and it is not*

possible to determine which baby will need intubation in the delivery room, it would be unrealistic to have the opportunity to obtain informed consent we will aim for "deferred consent" process. As this study only present minimal risk to the infants and the device being used is an FDA approved device for use in neonates, a deferred consent is being requested for from the IRB.

How much time to decide: Since study related interventions has already occurred and we are asking parents to give consent for using this information as well as review of electronic medical records parents will have adequate time to make this decision free of any coercion to participate in the study.

Person authorized to obtaining consent: All investigators, program coordinator associated with the study.

SUBJECT FEES: None

REIMBURSEMENT/RENUMERATION FOR PARTICIPTION: None

RISK BENEFIT ASSESSMENT

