Providing VTV to the VLBW infants is a standard of care practice upon admission to the NICU, with this study we seek to provide more physiologic VTV to the infant immediately after birth without any delay.

Phase I: No risk and no benefit directly to the patient, as this is the observational phase of the study. Information obtained from this phase study may potentially be beneficial by supporting the need for future studies in preterm infants with need for invasive respiratory support.

Phase II: Infants in intervention arm will receive the same routine care with additional information about the TV being delivered to the study infants. The provider's ability to adjust the PiP to provide goal TV may be potentially beneficial for the study infants, as in current DR practice the delivered tidal volume is unknown and infant may be receiving TV out of the set goal range. Infants in the control arm will not have any direct risk or benefit. The only concern would be adding less than 1ml of dead space with the flow sensor, which may or may not be of any clinical significance at all.

UNANTICIPATED PROBLEMS AND SERIOUS ADVERSE EVENT REPORTING

Unanticipated problems and serious adverse events to the subjects related to the study will be reported to the IRB within 48 hours of the occurrence.

RANDOMIZATION

Phase I: No randomization. All infants will receive pressure regulated breaths, 40-60 breaths/min, PiP of 20-24cm of H₂O as recommended by 2017 Neonatal Resuscitation Program (NRP) guidelines. Providers will be blinded from the measured TV during the resuscitation.

Phase II: All infants born <32 weeks will be randomized to one of the study group. Randomization will be via sealed envelope, opened in DR after the decision to intubate is made, with a 1:1 randomization ratio. To keep the gestational age in the two study arm relatively similar, as we are proposing only a small sample size for this current study, randomization will be stratified by gestation age group (Randomization subgroup I: <28 weeks and subgroup II: 28-32 weeks). Infants in both the arms will have a flow sensor at the ETT connected to Respironics NM3 monitor (Philips Healthcare, Eindhoven, Netherlands), to measure breath to breath TV.

INTERVENTION

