We will use the pilot phase to begin identifying and assessing the frequency of adverse events for developing safety measures. Additionally, the pilot data will be used to estimate effect sizes and variability so that sample size and statistical power may be computed for a later randomized control trial.

Although this study will not be powered to evaluate differences in longer term pulmonary outcomes like BPD, we will still assess for possible trends in difference of BPD and other pulmonary outcomes between the two groups. Being a feasibility study, this study will not be powered to evaluate the safety and other long term outcomes between the two arms, but we will collect and analyze the safety data especially since we will be using the enrolled patient data for the future randomized control trial.

VULNERABLE POPULATION

This study involves studying newborn infants, who are considered vulnerable population. In phase I, the subjects involved in the study will have minimal risks as they will receive standard of care practices and we will only assess our ability to measure the TV in this population. In Phase II, the control arm has minimal risk as they will receive standard of care practices. The intervention arm may potentially have direct benefit as with the information about TV during resuscitation, we can target our PiP for goal TV, thereby minimizing volutrauma and/or atelectotrauma. Thus, overall this study poses none to minimal risk for the study subjects and may potentially benefit the infants in the intervention arm.

For the Phase II the study related interventions will be done only after a written informed parental consent has been obtained.

DATA AND SAFETY MONITORING

Safety data will be monitored closely for all enrolled subjects with special focus on infants randomized to the intervention arm in Phase II. Subjects in the intervention arm, based on the tidal volume generated, the maximum PiP will be limited at 30cm of H₂O, as it would be considered unconventional to require more PiP than 30cm of water in the immediate neonatal phase for longer than 60 seconds duration. If the tidal volume cannot be measure within 60 second, the patients will continue to receive conventional PLV during the time eliminating any potential harm to the patient. We will monitor for development of any pulmonary complication in the enrolled subjects including but not limited to pneumothorax, pneumo-mediastinum, and pulmonary interstitial emphysema.

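### The deferred-consent section names no phase, conflicts with the Phase II prior-consent rule, and excludes infants with no tidal volume reading, which can inflate the Phase I feasibility rate

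*Combined protocol and SAP*

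**What the plan says.** Informed Consent Process and Timing sets out a single process and names no phase. Consent "is being requested after the birth of the child", and of prior consent the section says that "it would be unrealistic to have the opportunity to obtain informed consent". Parents are approached "only if the baby requires intubation in the delivery room and the TV measurements were obtained". On the time allowed for the decision, the section says: "Since study related interventions has already occurred and we are asking parents to give consent for using this information".

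Vulnerable Population gives a different rule: "For the Phase II the study related interventions will be done only after a written informed parental consent has been obtained".

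Four other places bear on this:

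- Selection of Subjects lists "Parental Consent" as an inclusion criterion, without saying when it must be in place.
- Experimental Design states that "Phase I will be an observational, non-interventional study".
- Randomization, for Phase II, states that "Randomization will be via sealed envelope, opened in DR after the decision to intubate is made". Allocation therefore comes before any tidal volume (TV) reading.
- Data Analysis defines Phase I feasibility as a TV reading in 80% of infants within 60 s of starting positive pressure ventilation through the tube. Specific Aims, for Phase II, asks for the share of infants in whom TV can be read and pressure then adjusted to reach the goal, and for the share who fail volume targeting and are switched.

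No section says how an infant with no TV reading is consented or kept in a denominator.

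**The concern.** There are two problems.

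The first is a conflict of rules. If the deferred process covers Phase II, an infant can be randomised and treated before consent, which Vulnerable Population rules out. Site staff could follow either section and cite the protocol.

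The second is selection on the outcome. Obtaining a TV reading is the feasibility endpoint in Phase I and part of it in Phase II. The consent sought is permission to use the delivery-room data and review records. If parents are approached only where a reading exists, failures of the most complete kind drop out of the result. Potential Pitfalls and Alternatives itself anticipates that the monitor may be unable to read the very small volumes of the smallest infants, so the never-measured group may not be empty and is unlikely to be a random subset.

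**Working it through.** **The plan's own figure.** The only calculated figure is the Phase II precision statement: at n = 30 the 95% interval is about 55% as wide as the standard deviation (SD). It reproduces as the chi-square interval for an SD: √(29/χ²₀.₀₂₅) − √(29/χ²₀.₉₇₅) = 1.344 − 0.796 = 0.548 SD. This point does not rest on it.

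**Consent timing, side by side.** The deferred section says that interventions have already taken place when parents are asked. The Vulnerable Population rule says that Phase II interventions wait for written consent. For Phase II both cannot hold. They are compatible only if the deferred section is confined to Phase I, which it does not say.

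**Effect of the reading condition in Phase I.** Inputs from the documents are 10 infants (Sample Size) and the 80% threshold (Data Analysis), that is, at least 8 of 10. Inputs assumed, because the documents give none:

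- s = share of all intubated infants measured within 60 s
- l = share measured, but later than 60 s
- f = share never measured, so that s + l + f = 1

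With every intubated infant in the denominator, the rate is s. With only infants who have a reading, it is s/(s + l) = s/(1 − f). The chance of meeting the threshold is the binomial probability of at least 8 of 10 at that rate. I assume that the sample is filled with 10 consented infants and that refusal is unrelated to the outcome.

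Worked example: s = 0.60 and half of the failures never measured, so f = 0.40 × 0.5 = 0.20. The observed rate is 0.60/0.80 = 0.75.

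- All infants: P(X ≥ 8 | 10, 0.60) = 0.167
- Only infants with a reading: P(X ≥ 8 | 10, 0.75) = 0.526

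| s | Share of failures never measured | f | Observed rate | P(≥ 8 of 10) |
|---|---|---|---|---|
| 0.60 | 0 | 0 | 0.600 | 0.167 |
| 0.60 | 25% | 0.100 | 0.667 | 0.299 |
| 0.60 | 50% | 0.200 | 0.750 | 0.526 |
| 0.60 | 100% | 0.400 | 1.000 | 1.000 |
| 0.70 | 0 | 0 | 0.700 | 0.383 |
| 0.70 | 25% | 0.075 | 0.757 | 0.546 |
| 0.70 | 50% | 0.150 | 0.824 | 0.747 |
| 0.70 | 100% | 0.300 | 1.000 | 1.000 |
| 0.80 | 0 | 0 | 0.800 | 0.678 |
| 0.80 | 50% | 0.100 | 0.889 | 0.909 |

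The rows with f = 0 show no bias.

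**Phase II, only if the deferred route applies there.** Let w be the true share of intervention infants who fail volume targeting, including the never-measured share f. The observed share is (w − f)/(1 − f), lower than w by f(1 − w)/(1 − f). The measurable-TV component is biased favourably in the same way. If lost infants are replaced, 30/(1 − f) infants must be randomised to retain 30: about 33 at f = 10% and 43 at f = 30% (assumed values).

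**The case against.** The strongest reply is that the two sections can be read together. Vulnerable Population gives a specific rule for Phase II, and a specific rule normally overrides a general one. Much of the deferred section fits Phase I: it asks to use data already collected, rests on minimal risk and on the device, and mentions neither randomisation nor pressure adjustment. The word intervention could loosely mean placing the flow sensor, which Phase I also does. This is a workable reading, and the consent form is not in the reviewed copy to settle it. But the text does not state it. Withdrawal criteria, randomisation, blinding and sample size are all split by phase, and the consent section is not. Its reason for deferral, that the need for intubation cannot be foreseen, applies equally to Phase II, and no procedure for prior consent is described.

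Three stronger readings are tempting, and the documents do not support them:

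- A reader might infer that 3 to 6 of 15 infants per arm are lost after randomisation (15 × 0.2 to 15 × 0.4, if 60–80% have a reading). That rate is not in the documents, the loss is zero if the Vulnerable Population rule governs Phase II, and unconsented infants might be replaced.
- A reader might infer that the Phase II measurable-TV result is 100% by construction. The stated objective also requires pressure to be adjusted to reach goal TV, and an infant with a reading can still miss it.
- A reader might infer that failures vanish altogether. Infants first measured after 60 s, and those who fail volume targeting after a reading, can still be consented and counted. Only never-measured infants are lost.

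**Conclusion.** The point stands in two parts. First, the consent sections are unreconciled: one describes deferral without a phase limit, and the other requires written consent before any Phase II intervention. Calling them irreconcilable would go too far, since confining deferral to Phase I would resolve the conflict, but the protocol has to say so.

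Second, approaching parents only after a reading selects on the feasibility outcome. This bears most directly on the Phase I 80% criterion, because on either reading the deferred process covers Phase I. The size depends wholly on the never-measured share, which the documents do not give. It ranges from no bias, when every failure is a late reading, to an observed 100%, when every failure is a never-measured infant. The intermediate case (75% observed for a true 60%, with the chance of passing at 53% instead of 17%) is an illustration, not an estimate. The Phase II effect is conditional on the deferred route applying there.

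**What to change.** - State one consent route for each phase, so that Informed Consent Process and Timing and Vulnerable Population agree. Which route applies in Phase II is for the sponsor and the IRB to decide.
- Delete the requirement for a TV reading from the condition for approaching parents.
- Approach the parents of every eligible intubated infant in Phase I and, if Phase II consent is deferred, of every randomised infant.
- Define the feasibility denominators in Data Analysis as all such infants, and count an infant with no TV reading as a failure.

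The cost is a wording change through the IRB, a few more consent approaches, and possibly a less favourable feasibility rate. The change is best made before enrolment, because infants whose parents were never approached cannot readily be recovered.

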With rapidly changing lung compliance in the immediate neonatal transition phase, PLV can lead to significant variability in the delivered TV. Recent reports suggests that pressure limited resuscitation devices routinely used in the delivery room are capable of tripling the intended TV while providing PPV in a newborn manikin^x. Large TV can lead to volutrauma, which is associated with adverse pulmonary outcomes. A study in preterm lambs showed as few as six large tidal volume breaths at birth can lead to acute lung injury and blunt the effect of subsequent surfactant treatment^{xi}. Ventilation with large breaths may cause gross overexpansion of regions that are forced open, leaving major parts of the lung blocked by fluid and unexpanded, and such regional over distension can be expected to cause epithelial and microvascular injury and pulmonary edema. The resultant pulmonary edema may make the lung more susceptible to further volutrauma during conventional mechanical ventilation^{xii}. Several animal studies have demonstrated that PPV with TV more than 8 mL/kg causes lung inflammation and lung injury^{xiii,xiv,xv,xvi}. Additionally, animal and human studies have demonstrated that excessive TV delivery during PPV in the delivery room causes brain inflammation and injury^{xvii,xviii,xix,xx}. Likewise, recent meta-analysis data demonstrate infants ventilated using volume targeted ventilation (VTV) modes reduce rates of death or BPD, pneumothoraces, hypocarbia, severe cranial ultrasound pathologies and reduce the duration of ventilation compared with infants ventilated using PLV modes. The risk of lung injury is in all likelihood related to the magnitude of the volutrauma at birth, and therefore ventilation immediately after birth needs to be very gentle^{xii}.

Without information about TV in the DR and rapidly changing lung compliance, PLV may lead to volutrauma. But no study has specifically evaluated the ability to measure TV provided in intubated infants in the DR or aimed at performing VTV in the DR while assessing its potential role in reducing lung injury.

INNOVATION

With recent advances in technology and ability to measure small TV at the endotracheal tube (ET) level with the help of flow sensors, TV can be measured accurately at the ET tube level and volume targeted ventilation (VTV)

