Phase II: We will enroll a total of 30 patients (15 per study group). The sample size was selected to insure sufficient number of patients to estimate variability and effect sizes^{xxi} and to estimate recruitment rates. For example, with 30 patients, the width of the 95% confidence will be about 55% as wide as the standard deviation. This estimate will help develop sample size estimates for future studies.

DATA COLLECTION AND STORAGE

Study data will be collected and managed using a secure, web-based, password protected RedCap (Research Electronic Data Capture) data base^{xxii}. Baseline demographic maternal and infant characteristics, TV, PiP, mean airway pressure, PEEP, FiO₂, resuscitation details, duration of invasive mechanical ventilation, duration of non-invasive respiratory support (non-invasive mechanical ventilation, continuous positive airway pressure), duration of oxygen treatment, home O₂ requirement, BPD incidence and severity along with pulmonary complications will be collected. Standard BPD definition of mild (oxygen use for 28 days), moderate (oxygen need at 36 weeks), or severe (ventilatory support at 36 weeks), along with physiologic BPD testing at 36 weeks will be used to define BPD. This data will also be used prospectively in a future randomized control trial if feasibility study is successful. The research team members and DSMB will have access to the full data set.

DATA ANALYSIS

As the study is designed as a pilot, no formal tests of hypotheses will be conducted^{xxiii}. In Phase I, our goal is to attain skill and competency with using the device, as well as to establish that our measures are reliable and valid. Descriptive statistics will be use to assess the feasibility of measuring TV in the DR. Feasible will be defined as being able to successfully measure the TV in 80% of the infants within 60 seconds of starting PPV via the endotracheal tube.

For Phase II of the pilot project, data analysis will be limited to point estimates (e.g., means and proportions). We will describe the feasibility of using VTV in the DR, and data analysis will be limited to estimating the point estimates (e.g., means and proportions) and variability of ventilatory measures in each group and overall. We will also estimate recruitment and attrition rates, as well as the duration of the consenting process.

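### The protocol names brain injury as a harm of excessive tidal volume, but no brain outcome is prespecified or systematically collected in either Phase II arm

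*Combined protocol and SAP*

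**What the plan says.** **The harm.** The SIGNIFICANCE section of the Combined protocol and SAP says, from animal and human studies, that "excessive TV delivery during PPV in the delivery room causes brain inflammation and injury". It then cites meta-analysis data in which VTV lowered several outcomes, among them "pneumothoraces, hypocarbia, severe cranial ultrasound pathologies and reduce the duration of ventilation compared with infants ventilated using PLV modes". One reference cited there, by its title, relates delivered tidal volume at birth to intraventricular haemorrhage in preterm infants.

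**What Phase II records.**
- The Aim #3 objectives under SPECIFIC AIMS include "To assess the incidence of complications including pneumothorax" and "To evaluate for other unexpected adverse events that may be associated with VTV". The longer-term outcomes listed there are all pulmonary.
- The DATA COLLECTION AND STORAGE list opens with "Baseline demographic maternal and infant characteristics, TV, PiP, mean airway pressure, PEEP, FiO₂, resuscitation details", continues through durations of respiratory support and oxygen, and ends with "BPD incidence and severity along with pulmonary complications will be collected".
- DATA AND SAFETY MONITORING says "We will monitor for development of any pulmonary complication in the enrolled subjects including but not limited to pneumothorax" and adds two other air-leak conditions.

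**What Phase II is meant to conclude.** The outcome and implications paragraph after the opening aims expects a successful pilot to show that VTV is safe as well as feasible. STATEMENT OF PURPOSE makes the absence of extra complications relative to PLV part of a successful Phase II. DATA ANALYSIS says the pilot will start to establish adverse-event frequencies and that enrolled infants' data will be used in the later trial.

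**The concern.** The rationale gives the exposure under study one specific non-pulmonary harm, and names a measurable form of it that is said to differ between the two ventilation modes being randomized. The outcome lists then leave it out. A safety statement drawn from those lists would describe air leaks and chronic lung disease by arm, with no planned information on the brain. This works in both directions: a reduction in brain injury with VTV could be missed as easily as an increase. The gap would also carry forward, because the later trial is to draw on this pilot for event frequencies and is to use these infants' data.

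**Working it through.** The documents give no figure for brain injury. Their only precision statement is an interval width of about 55% of the standard deviation with 30 patients. It reproduces as the 95% chi-square interval for a standard deviation at n = 30: limits 0.796 and 1.344 SD, width 0.548 SD. It concerns continuous measures and has no bearing here. The check is therefore mainly a reading of every Phase II list.

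**Step 1: is a brain outcome named?**

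| Place | Coverage | Brain outcome named? |
|---|---|---|
| Aim #2 objectives | Tidal volume, pressures, oxygen, blood gases (pH, PCO2) | No |
| Aim #3 objectives | Resuscitation time, Apgar scores, oxygen, complications, unexpected events, pulmonary morbidity | No |
| DATA COLLECTION AND STORAGE | Baseline data, ventilation and oxygen variables, resuscitation details, BPD, pulmonary complications | No |
| DATA AND SAFETY MONITORING | Pulmonary complications | No |
| Subject stopping rules | Air leak, high inspiratory pressure, persistent low saturation or bradycardia | No |

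**Step 2: could a brain event enter another way?** Yes, by four routes.
- *The complications objective in Aim #3.* It is open-ended, with pneumothorax as its only example. The data list, however, has a field only for pulmonary complications.
- *The unexpected-events objective in Aim #3.* It is not limited by organ, but it is tied to VTV. An excess of brain injury under VTV could qualify as unexpected, since the rationale predicts the reverse. Brain injury after uncontrolled tidal volume in the PLV arm is neither unexpected nor associated with VTV.
- *Serious adverse events.* UNANTICIPATED PROBLEMS AND SERIOUS ADVERSE EVENT REPORTING covers events related to the study, whereas DATA AND SAFETY MONITORING covers any serious event. Both are duties to report to the IRB. Neither says how brain findings are to be ascertained.
- *Adverse-event frequency in DATA ANALYSIS.* This is a stated purpose without a defined data item.

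**Step 3: would capture be equal by arm?** Providers are unblinded (BLINDING, Phase II), safety monitoring gives special focus to the intervention arm, and one of the routes applies to VTV only. If the true rate is p in both arms and the chance that a case is recorded is c1 under VTV and c2 under PLV, the expected recorded counts differ by 15 × p × (c1 − c2). Nothing in the plan makes c1 equal c2.

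**Step 4: would the field hold data?** Rates are assumed, and every infant is taken as scanned. Expected cases in an arm are 15p. The chance of at least one case among n infants is 1 − (1 − p)^n.

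| Assumed p | Expected cases in 15 | At least one in 15 | At least one in 30 |
|---|---|---|---|
| 5% | 0.75 | 54% | 79% |
| 10% | 1.5 | 79% | 96% |
| 20% | 3 | 96% | 99.9% |
| 30% | 4.5 | 99.5% | >99.9% |

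**Step 5: what could the data support?** With zero cases, the upper limit of the two-sided 95% exact interval is 1 − 0.025^(1/n). This is 21.8% for an arm of 15 and 11.6% for all 30. Description is possible; reliable comparison of the arms is not.

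**The case against.** The strongest reply is that the plan is not closed to brain events. The complications objective is open-ended, any serious adverse event goes to the IRB, and DATA ANALYSIS undertakes to collect and analyze safety data while disclaiming power for it. With 15 infants per arm, an added field would not allow a reliable comparison. All of this is right, and it limits the point to unsystematic capture. It does not remove it: the plan accepts the same lack of power for BPD and other safety outcomes and collects those anyway.

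A reader might infer more than the documents support:
- *That the pilot cannot see brain injury, or would record no case.* The routes in Step 2 contradict this.
- *That every listed item is respiratory.* Apgar scores, baseline characteristics and bradycardia are listed, although none of them measures brain injury.
- *That hypocarbia is also overlooked.* Aim #2 compares PCO2 between the arms.
- *That VTV carries more brain risk because its pressure limit is 30 cm H2O against 20-24 in controls.* The 30 is a ceiling, with pressure adjusted toward a tidal-volume goal, and the harm named is excessive volume. The comparison does not show more excessive volume under VTV.
- *That Phase I has the same gap.* Phase I is observational, and its aims are to measure tidal volume and its variability; it draws no safety comparison.

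**Conclusion.** The point holds in a limited form. No brain outcome is prespecified or systematically collected in either Phase II arm, although the protocol's own rationale names brain injury as a harm of the exposure and cites a cranial ultrasound outcome as differing between the two modes. Rates by arm could not be reliably described, so the planned statement that VTV is safe would rest mainly on pulmonary events. The primary feasibility outcome is unaffected, and the documents give no basis for saying which arm would have more brain injury. Calculations using event rates are illustrative, because those rates are assumed. This is a worthwhile, low-cost addition, not a flaw that invalidates the pilot.

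**What to change.** For both Phase II arms, add two items to the DATA COLLECTION AND STORAGE list and to the Aim #3 complications: the worst intraventricular haemorrhage grade, and any white-matter injury, on cranial ultrasounds done for routine care up to 36 weeks or discharge. The data collector, who is already to be blinded to allocation under BLINDING, takes them from the radiology report. Code infants without a scan separately from infants with a normal scan. Report counts by arm with the number scanned as denominator, descriptively and without a between-arm test, in line with DATA ANALYSIS.

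The cost is one or two database fields and some chart abstraction. No procedure is added, and the consent process already covers review of medical records. The downside is dependence on scans done for care. That such scans are routine in these infants is an assumption, since the documents do not mention them. If few infants are scanned, or scanning differs by arm, the result must be read with that in view. Even with complete scanning, 15 per arm will not support a reliable comparison.
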